
Currently, there is rapidly growing interest in the development of cannabis and cannabinoid-based medicines for the treatment of myriad health conditions. THC (dronabinol) has been approved by the FDA for over 30 years, yet is rarely used in medicine. Part of the reason for that is because the therapeutic index of pure THC, when given intravenously (D'Souza et al. 2004) or orally (Favrat et al. 2005) is narrow, especially among individuals previously naïve to its effects. Acute overdose incidents involving THC or THC-predominant cannabis commonly include anxiety, panic reactions or toxic psychoses, for which no pharmacological intervention is generally necessary, but which can result in significant and sustained discomfort to the individual. In recent years, advocates for cannabis legalization have argued that the use of cannabis (versus pure THC) reduces the rate and severity of adverse effects in the treatment of medical conditions, and this argument has been the basis for establishing medicinal cannabis laws in 34 of the 50 U.S. states and the District of Columbia.

To date, scientific evaluation of the "entourage" effects of cannabis versus THC alone have been largely limited to the study of cannabidiol (CBD) as a compound purported to attenuate

some of the untoward psychoactive effects of THC and generally reduce its adverse event profile. Clinical research by a UK pharmaceutical company suggests that producing cannabinoid medicine with a 1:1 ratio of THC:CBD produces better clinical results with fewer side effects relative to higher THC:CBD ratios (Russo and Guy 2006). However, laboratory studies have failed to detect a modulatory effect of CBD on the subjective effects of THC (Ilan et al. 2005, Haney et al. 2016). Though there is a lack of controlled research, numerous reports in published literature dating back to the 10th century indicate that the consumption of acetylcholinesterase inhibitors (e.g., Calamus root) have been utilized as an antidote to THC intoxication via inhalation of cannabis or hashish (Russo, 2011). In addition, cannabis retailers often advertise that cannabis containing high concentrations of pinene can serve as a memory enhancer. Thus, pinene could conceivably help counteract the well-documented acute working and episodic memory impairments induced by THC and/or cannabis, though this has never been examined empirically.

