contain 0.5mg of pinene and as high as 5mg of pinene. Importantly, 1 gram is the amount of plant material commonly used to make a single cannabis cigarette ("joint" or "blunt"). Thus, these doses are ecologically relevant and have demonstrated safety with respect to acute dosing via direct inhalation. The additional 15mg dose of pinene is higher than what would typically be consumed in 1 g of natural cannabis, but reflects the current practice in the cannabis industry in which terpenes are extracted from cannabis separately from cannabinoids and then reconstituted at unnatural ratios. The addition of the 15mg pinene dose is an amendment to the original protocol, at which time no adverse effects had been reported following either 0.5mg or 5mg pinene doses for the first 13 randomized participants and exposure to both doses of pinene did not differ from placebo on any pharmacodynamic outcomes assessed.

The results of this study will represent a significant initial advancement in understanding the behavioral pharmacology of cannabis. This is the second study in a series of similar experiments funded by NIH in which we will begin to systematically evaluate the interactions of multiple components of the cannabis plant. The first study (IRB00085652) showed that the terpene limonene exhibited a dose-orderly reduction in the acute anxiogenic effects of high doses of THC. In that study, as in this one, small effects were observed at low and medium doses (1mg and 5mg limonene), but 15mg limonene significantly reduced anxiety, paranoia and similar subjective effects compared with 30mg THC in the absence of limonene. Notably, the 15mg limonene dose also exceeded the amount typically found in a 1g cigarette of natural cannabis, so there is precedent from this prior study in needing to increase the maximum dose of terpenes in order to observe robust effects on target endpoints. Characterization of the interaction between THC and pinene will provide an initial scientific basis for whether or not there is benefit for including terpenoids in the development of cannabinoid-based pharmaceutical products as one means of reducing the incidence and/or severity of side effects.

4. Study Procedures

a. Study design, including the sequence and timing of study procedures (distinguish research procedures from those that are part of routine care).

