Protocol Overview. The proposed study will be conducted at the Johns Hopkins Behavioral Pharmacology Research Unit (BPRU). The purpose of the study is to examine the behavioral pharmacology of THC, pinene, and their combination versus placebo. All procedures will be performed in double-blind manner using a within-subject crossover design. Participants will be healthy adults between the ages of 18 to 55. A total of 6 outpatient drug administration sessions will be conducted for each evaluable participant.

- 1) Placebo (ambient air)
- 2) THC (30 mg)
- 3) Pinene (15 mg)
- 4) THC (30 mg) + Pinene (0.5 mg)
- 5) THC (30 mg) + Pinene (5 mg)
- 6) THC (30 mg) + Pinene (15 mg)

We will obtain a battery of pharmacodynamic outcome measures at baseline and for 6 hours after each dose. Sessions will be conducted at a target rate of 1-2 times per week, with a minimum of 2 days between experimental sessions. We will recruit study volunteers until 20 participants complete the protocol. Participants who drop out of the study prior to completion of

all scheduled sessions will be considered "incomplete" and will be replaced. Drug administration sessions will be completed in a randomized order.

Participants. We will recruit and consent up to 75 research volunteers in order to obtain 20 study completers. This will exclude 3 pilot participants who completed the study using lower THC doses (10 and 25mg). Participants who completed the study prior to the addition of the 15mg pinene doses will be invited to return to the lab to complete the two new dose conditions (15mg pinene and 30mg THC + 15mg pinene). We anticipate that about 50% of those screened will not be eligible or interested in the study, and that post-randomization some participants may drop out of the study before completion. It is estimated that we will need to randomize 40 participants to achieve 20 completers given the length of the protocol.

The target demographic for study participation are healthy adults who: have a history of intentionally consuming cannabis, have not used cannabis more than an average of twice per week in the 3 months prior to study participation, and who are not currently dependent on or seeking treatment for use of cannabis or other drugs, including alcohol.

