Detailed instructions for use of the device are available here: https://www.storzbickel.com/media/wysiwyq/CRAFTY-MIGHTY/PDF/mighty-vaporizer-instructions-manual.pdf (see annex documents) and are provided in the supplementary materials section of the IRB application. Participants will inhale the contents of one Mighty Medic dosing capsule. Specifically, they will be given 15 minutes to inhale the contents of the capsule ad libitum (i.e., at their own pace). Participants will take a minimum of 15 puffs, and if a visible vapor is still observed after 15 puffs, they will continue to take puffs until they no longer exhale visible vapor (this signifies that the dosing capsule is depleted; see detailed instructional materials from Stortz and Bickel). Following each puff, participants will exhale vapor into a hand-held smoke filter; this will ensure that neither the study participants or research staff see the exhaled vapor. We have found in our ongoing study with a different terpene (limonene) that the visibility of exhaled vapor can differ between pure THC, pure terpenes, and placebo. Overall, the puffing procedure will produce THC exposure of 0 or 30mg THC, and alpha-pinene exposure of 0.5mg, 5mg, or 15mg. Participants will be able to halt self-administration of the study drug if they experience adverse effects prior to inhaling the entire dose. Similarly, study staff may halt the drug administration procedure if untoward drug effects are observed. This is not expected at the doses under investigation, but may occur in rare circumstances. Study participants and research staff will be blinded to dose assignment. The conclusion of drug administration will be considered the "0 hour" by which remaining protocol assessments will be scheduled. To prevent issues of crosscontamination, new dosing pods and mouthpieces will be used for every test session, and the vaporizer will be disassembled and thoroughly cleaned according to manufacturers recommended methods between study participants.

Post-Drug Administration Procedures.

Following the "0-hour" time point (last exhalation of study drug), participants will complete a battery of assessments that includes:

- 1) Serum specimen collection at 0min, 15 min, 60 min, 120 min, and 180 min.
- 2) Subjective drug effect and mood ratings on computerized questionnaires and vital signs assessments at 0 min, 15 min, 30 min, 60 min, 90 min, 120 min, 180 min, 240 min, 300 min, and 360 min.

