c. Blinding, including justification for blinding or not blinding the trial, if applicable.

THC/terpenoid dose assignment will be double-blinded in this study. That is standard procedure for appropriate scientific control in studies evaluating the dose effects of psychoactive drugs.

d. Justification of why participants will not receive routine care or will have current therapy stopped.

e

Participants in this study will be healthy volunteers. Routine care for any medical illness that may arise during participation will not be affected.

f. Justification for inclusion of a placebo or non-treatment group.

A placebo dosing session (no THC, no pinene) will be included to help interpret active drug effects on pharmacodynamic outcomes. Placebo dosing provides a control for expectancy effects on subjective reports and cognitive performance as well as non-pharmacological factors such as fatigue, hunger, and learning effects on performance tasks. Placebo dosing is standard for research studies involving evaluation of acute drug effects.

g. Definition of treatment failure or participant removal criteria.

This is not a treatment study. Participants may quit participation at any time of their own volition. The study investigators will discharge study participants for failing to attend their scheduled session, failure to follow the protocol requirements, or for other reasons not known at this time.

h. Description of what happens to participants receiving therapy when study ends or if a participant's participation in the study ends prematurely.

This is not a treatment trial; there is no direct course of therapy related to the participant population being targeted. We are recruiting healthy adults with experience using cannabis and who are not seeking treatment for substance use problems. Should any report the desire for treatment they will be referred to appropriate community service centers. Premature termination of participation may result in the need to recruit additional research volunteers, but should have no impact on the study volunteer directly.

5. Inclusion/Exclusion Criteria

Participants will meet the following eligibility criteria: Inclusion Criteria

- 1. Have provided written informed consent
- 2. Be between the ages of 18 and 55
- 3. Be in good general health based on a physical examination, medical history, vital signs, and screening urine and blood tests

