The primary benefit of the proposed research is in the knowledge gained regarding the pulmonary inhalation of THC and pinene alone and in combination. This knowledge will advance our basic scientific understanding of both substances and may guide policy and regulations related to cannabis. The study will also extend the extant literature investigating the acute dose effects of inhaled THC, including subjective effects, cognitive performance, and their correlation with biological cannabinoid levels. These experiments may objectively demonstrate synergy of cannabis components and the modulating and even beneficial effects of cannabis terpenoids on THC. The results could benefit the research community in finding and developing selected cannabis chemovars with unusual cannabinoid and terpenoid contents and ratios for improved efficacy and optimized therapeutic index. Because we anticipate relatively minor risks to these cannabis experienced study participants, we feel that the proposed research has a positive risk-benefit ratio.

9. Payment and Remuneration

 Detail compensation for participants including possible total compensation, proposed bonus, and any proposed reductions or penalties for not completing the protocol.

All participants will be compensated \$30 for completing the screening assessment, up to \$1800 for completing each of 6 outpatient sessions, and \$500 in completion bonuses resulting in \$2330 of total possible earnings for completing the entire study. Compensation of this magnitude is appropriate given the length and nature of this study. Calculations are as follows:

Screening Visit: \$30

Outpatient Sessions 1-6: \$300/day (\$1800 total)

Completion Bonus: \$500

Total Compensation: \$2330

Study participants will receive an additional \$300 for any test session that is repeated due to data loss or for participants invited back to completed additional doses added as a study amendment. There will not be any change to the study completion bonus for repeat testing.

10. Costs

a. Detail costs of study procedure(s) or drug (s) or substance(s) to participants and identify who will pay for them.

The only direct costs to the participants will be their transportation to and from Bayview for each study visit. That cost has been factored into the compensation for participating.

Reference List

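### Participants recalled after the amendment are scheduled only for the two 15 mg pinene conditions, so their pinene dose is fixed by design and the unqualified double-blind statements need an exception

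*Combined protocol and SAP*

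**What the plan says.** Section 4.a (Protocol Overview) lists six conditions, taken in random order: placebo, 30 mg THC, 15 mg pinene, and 30 mg THC with 0.5, 5 or 15 mg pinene. Under Participants, those who finished before the 15 mg doses were added "will be invited to return to the lab to complete the two new dose conditions (15mg pinene and 30mg THC + 15mg pinene". Section 9 sets a further $300 per session "for participants invited back to completed additional doses added as a study amendment". Nothing in the text adds placebo, THC alone or a lower pinene dose to the return visits, or says what returners or session staff are told about the recall.

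The blind is stated three times without exception:
- Section 4.a, Protocol Overview: "All procedures will be performed in double-blind manner using a within-subject crossover design".
- Section 4.a, Experimental Drug Exposure: "Study participants and research staff will be blinded to dose assignment".
- Section 4.c: "THC/terpenoid dose assignment will be double-blinded in this study".

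The masking measures described are the choice of vapour over smoke and a hand-held filter that hides exhaled vapour. Section 4.f adds: "Placebo dosing provides a control for expectancy effects on subjective reports and cognitive performance".

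The Background says the 15 mg dose was added when 0.5 and 5 mg had shown no pharmacodynamic difference from placebo. The safety record it cites at that point is "for the first 13 randomized participants". It also cites the laboratory's limonene study as precedent for raising the top terpene dose to see an effect.

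**The concern.** Pinene is the only component that separates THC + 15 mg pinene from THC alone. In the return visits it does not vary, so knowing that a session is an added-dose session is the same as knowing the pinene dose. Hiding the vapour does not help, because the set of possible conditions gives the dose away. A returner's THC-alone session was run earlier, in a sequence that included pinene-free sessions. The two sides of the contrast may therefore have been run under different degrees of masking, and adjusting for session position would not restore the blind.

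The amendment was made to test the 15 mg dose, so this is the contrast that matters most. Section 4.f accepts that expectancy can act on subjective reports and on cognitive performance, but the return visits contain no placebo session. The Background notes that "cannabis retailers often advertise that cannabis containing high concentrations of pinene can serve as a memory enhancer", which suggests the direction expectancy might take. The outcomes most exposed are the self-rated secondaries: the trouble-with-memory item of the Drug Effect Questionnaire and the POMS confusion subscale.

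**Working it through.** **1. What a session can contain (conditions in Section 4.a).**

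| Session type | Possible conditions | Without pinene | With 15 mg pinene |
|---|---|---|---|
| Current six-session schedule | 6 | 2 | 2 |
| Return sessions | 2 | 0 | 2 |

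The first row describes participants who take all six conditions. The documents do not list the schedule that returners followed before the amendment, so no before-and-after probability can be given for them. In the first return session THC remains masked (1 of 2). The second can be deduced only if the first is recognised. That adds little here, because THC is present on both sides of the contrast.

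**2. How many completers could be affected.** I take the 13 in the Background as everyone randomised when the dose was added, and 20 completers from Section 4.a.
- Ceiling: 13/20 = 65%, if all 13 completed, returned and count towards the 20. Six-session participants are then 20 − 13 = 7.
- Illustration: Section 4.a expects 40 randomised for 20 completers, or 50%. Then 13 × 0.5 = 6.5, so 6 or 7 of 20 (30% to 35%). This borrows a rate planned for the present protocol and assumes that every earlier completer returns. It is not a best estimate.

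**3. What a shift in returners could do.** The documents give no size for an expectancy effect, so the shift b below is an assumption, in units of the SD of the paired difference. The mean bias is (r/20) × b for r returners. Type I error comes from 100,000 simulated paired t-tests with n = 20, two-sided alpha 0.05 assumed.

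| Returners r | b | Mean bias | Type I error |
|---|---|---|---|
| 6 | 0.2 | 0.06 | 5.7% |
| 6 | 0.5 | 0.15 | 9.1% |
| 6 | 0.8 | 0.24 | 14.4% |
| 13 | 0.2 | 0.13 | 8.4% |
| 13 | 0.5 | 0.325 | 26.5% |
| 13 | 0.8 | 0.52 | 53.9% |

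**4. Precision of a split by return status.** Study Statistics calls 20 adequate for effect sizes of 0.87 to 1.0 but states no alpha or power, so there is no power figure to reproduce. I assume two-sided 0.05 and effect sizes in SDs of the paired difference. The paired t-test then has noncentrality d√n:
- n = 20: power 95.8% at d = 0.87 and 98.9% at d = 1.0.
- n = 7: power 48.9% and 60.0%.

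The 95% interval half-width is t/√n: 2.093/√20 = 0.47 SD for 20 people and 2.447/√7 = 0.92 SD for 7. For the difference between 13 returners and 7 six-session participants it is 2.101 × √(1/13 + 1/7) = 2.101 × 0.469 = 0.98 SD.

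**The case against.** The strongest reply is that the documents do not show that any returner knew. The consent pages are not in the public file, and Section 9 is protocol text, not a script read to participants. Section 4.b allows sessions to be repeated after data loss or a protocol deviation, and Section 9 pays the same $300 for those. A recall alone therefore does not tell a participant that pinene is certain. This stands as regards participants' actual awareness. It does not rescue the blanket statement, because staff who know the protocol and the reason for the recall can infer the dose, and no safeguard for return sessions is described.

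It is also fair to say that the primary outcome is a count of correct PASAT answers, in participants trained to a stable baseline and screened for competency. An effect of expectancy on that count is conjecture. So is its direction: retailer advertising is not evidence of what these participants believed.

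A reader might infer that the double blind fails for the 15 mg contrast in the trial as a whole. The documents do not support that. Participants randomised to all six conditions keep the stated blind on this point, and they are at least 7 of 20 under the count above.

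**Conclusion.** The point holds for returners only. Following the plan as written fixes 15 mg pinene in every return session, so the unqualified double-blind statements are not correct for pinene in those sessions. The comparison of THC + 15 mg pinene with THC alone is partly compromised for at most 13 of 20 completers. That ceiling assumes that only people randomised by the time of the amendment can be returners.

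Confidence is high about the schedule. It is lower about whether anyone used the information, and there is no document-based estimate of the effect on results. The type I error figures show sensitivity to an assumed shift and are not a prediction. A reader might also take 65% as the share of the contrast that is unblinded, or conclude that PASAT scores were biased. The documents support neither: the number of returners is not given, and bias in an objective score has not been shown.

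**What to change.** 1. In Sections 4.a and 4.c, qualify the double-blind statement for return sessions: the pinene dose is fixed there, and only the presence of THC is masked. State what returners and session staff are told about the reason for the recall. This costs wording only.
2. Keep the full-sample analysis. Pre-specify a sensitivity analysis of THC + 15 mg pinene versus THC alone by return status, giving the number, estimate and confidence interval for returners and for six-session participants, on the PASAT and on the self-rated secondaries. This costs one extra display.
3. Do not describe a 15 mg effect as double-blind evidence unless the six-session participants show a consistent estimate. Define consistency in advance by the direction and size of the estimate with its interval. A significance test in a group that may number 7 would miss an effect of 0.87 about half the time.

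The price is low precision: with 13 returners, a difference between the groups smaller than about 1 SD could not be ruled out. A difference, if seen, would also mix masking with the later timing of the return sessions, so the split is a check and not a proof.

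I would not rest the whole 15 mg conclusion on the six-session subset, since it may be too small to carry it. Nor do I propose adding sessions to the return visits, which would mean extra dosing of volunteers and extra resources.
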